#### Questionnaires (participant completed)\*\*\*

- EQ-5D-5L
- Cough visual analogue scale (VAS)
- Living with Pulmonary Fibrosis (L-PF) questionnaire
- Health/social care Resource Use Questionnaire
- Patient Global Impression of Severity (PGI-S) Scale

\*\*\*Where possible, all questionnaires should be completed electronically during the clinic visit; if any technical issues occur, or if the participant requests it, paper copies of the

questionnaire can be used. If the participant is unable to complete the questionnaires during their clinic visit there will be an option for them to complete at home.

## 7.6. Randomisation

The randomisation sequence, using variable block sizes, will be generated by an unblinded statistician and implemented through the bespoke web-based randomisation service provided by the Centre for Healthcare Randomised Trials (CHaRT), ensuring allocation concealment and replicability. Blinded kit lists will be generated by an unblinded statistician and provided to CHaRT before the trial is open to recruitment.

Randomisation of a participant can take place after informed consent, once all the prescreening and baseline assessments have been completed and the participant's final eligibility has been confirmed. Eligibility must be assessed and confirmed by the PI or an appropriately qualified and delegated medically qualified doctor before a participant is randomised. Participants will then be randomised, using block randomisation, on a 1:1 basis to either prednisolone or placebo. Randomisation can occur the same day as the baseline assessments are completed if all information is available to make a final assessment of eligibility, or at most within a 7-day period from the date of the baseline assessment visit.

Participants will be randomised into the trial by a delegated member of the site team using an online randomisation service.

## ONLINE ACCESS FOR 24-HOUR RANDOMISATION

Further information on how to randomise can be found in the separate 'Randomisation' work instruction contained in the Investigator Site File.

In any case where technical issues prevent the site team from accessing the online randomisation service, ExeCTU staff will be available within office hours to randomise on behalf of a delegated member of the site team. Please note no ExeCTU back-up will be available out of office hours or on University of Exeter closure days (sites will be notified of these dates ahead of time).

Once the online randomisation process is complete, the system will indicate to the user the blinded IMP kit IDs which should be dispensed to the participant. It will not indicate whether the participant has been allocated to receive IMP or placebo, as the allocation will be blinded to participants, research teams and pharmacists at sites and the trial team at ExeCTU (with the exception of the unblinded statisticians and authorised members of the ExeCTU trials team who will have no role in the day-to-day management of the trial).

The online randomisation system will automatically send an email to ExeCTU and the site research team, including the PI and pharmacy staff, confirming the randomisation has taken place and the kit IDs allocated. Site staff should note in the medical records that the patient has been enrolled into the trial. Site staff will then complete and send the approved letter to the participant's GP (e.g. via post or secure email) informing the GP that their patient has entered the trial.

## 7.7. Blinding

This trial will be double-blinded and therefore neither research teams at sites nor participants will know which treatment has been allocated. This will be achieved by the IMP manufacturer over-encapsulating, packaging, and labelling the IMP and placebo doses to look identical. The IMP/placebo packs will be labelled with blinded kit IDs and the randomisation system will automatically assign a kit ID to be dispensed to the participant after randomisation is complete. Only the unblinded statisticians, the IMP manufacturer and the developers of the

randomisation system will have access to the master list which will indicate which pack IDs relate to placebo packs and which relate to prednisolone packs.

With the exception of the unblinded statistician(s) and authorised members of the ExeCTU trials team who will have no role in the day-to-day management of the trial. Where possible, all other members ExeCTU trials team will remain blinded.

## 7.7.1. Emergency unblinding

A trial-specific procedure is in place for emergency unblinding; this will be available 24/7 via a dedicated and automated phoneline. Further details will be provided in a separate unblinding work instruction.

If the person requiring the unblinding is a member of the investigating team, then a formal request to the PI or other delegated member of the team will be made who will then call the phoneline to trigger the unblinding.

Although the safety of the trial participants must always take priority, maintenance of the blinding is crucial to the integrity of the trial. Unblinding is strongly discouraged and should only occur for medical or safety reasons. Investigators should only break the blind when information about the participant's trial treatment is clearly necessary and will alter the appropriate medical management of the participant.

An assessment to unblind should be made in consultation with the clinical and research teams wherever possible. The treating clinician has the ultimate decision and right to unblind the participant.

## ACCESS FOR 24-HOUR UNBLINDING

Further information on how to unblind can be found in a separate 'Unblinding' work instruction in the Investigator Site File.

Each time an unblinding occurs, an email alert will be sent to ExeCTU and the site team, informing them that the unblinding has happened (this email will not reveal the allocation). A member of the site team should document the details of the unblinding and reasons for it on the 'Unblinding' eCRF and in the medical notes.

Following an emergency unblinding the participant should be treated according to the treating clinician's assessment.

Trial oversight committees, where required within their charters, will also be notified of any unblinding.

#### 7.8. Follow-up assessments

#### 7.8.1. Telephone follow up visits

All participants will be contacted via telephone\* at week 4 and week 8 post-randomisation; this is a safety precaution during the IMP dose reduction phase of the treatment schedule. During these calls, delegated research team should ask the participant if they have experienced any adverse events, if there have been any changes to their concomitant medications and the participant's self-reported IMP compliance (please see trial assessments in section 7 and assessment of compliance in section 8.11).

\*Please note if there any safety concerns the participant can be seen in clinic for these visits.

## 7.8.2. In person follow up visit

All participants will be asked to attend an in-person visit at week 12 post-randomisation (-14 days /+7 days) with a delegated member of the site research team. During this visit participants will return their unused IMP dispensed at the baseline visit and will be prescribed and dispensed a new supply of IMP (see section 8.6.1).

Data to be collected during this visit will include:

- Pulmonary function measurements
  - Spirometry: forced vital capacity (FVC)
- Participant's self-reported IMP compliance and dose modifications review
- IMP prescribed and dispensed
- Unused IMP collected from participant and returned to pharmacy for the purpose of safe disposal
- Adverse event review
- Concomitant medication review
- Additional immunosuppressant or antifibrotic medication review

## Questionnaires (participant completed)\*

- EQ-5D-5L
- Cough visual analogue scale (VAS)
- Living with Pulmonary Fibrosis (L-PF) questionnaire
- Health/social care Resource Use Questionnaire
- Patient Global Impression of Severity (PGI-S) Scale

\* Where possible, all questionnaires should be completed electronically during the clinic visit; if any technical issues occur, or if the participant requests it, paper copies of the questionnaire can be used. If the participant is unable to complete the questionnaires during their clinic visit there will be an option for them to complete at home.

## 7.8.3. End of treatment in person follow up visit

All participants will be asked to attend an in-person end of treatment visit at week 26 postrandomisation (-14 days /+ 7 days) with a delegated member of the site research team. During this visit the participant will be prescribed and dispensed IMP prednisolone/ placebo 1mg to complete the weaning phase (see section 8.6.2).

Data to be collected during this visit will include:

- Pulmonary function measurements
  - Spirometry: forced vital capacity (FVC)
  - Gas transfer: DLco/TLco
- IMP prescribed and dispensed
- Participant's self-reported IMP compliance and dose modifications review
- Check with participant has sufficient prednisolone/ placebo 5mg capsules to start weaning period (they will continue their 5mg supply dispensed at week 12 follow up visit)
- Waist circumference and weight
- Adverse event review
- Concomitant medication review
- Additional immunosuppressant or antifibrotic medication review

#### Questionnaires (participant completed)\*

- EQ-5D-5L
- Cough visual analogue scale (VAS)
- Living with Pulmonary Fibrosis (L-PF) questionnaire
- Health/social care Resource Use Questionnaire
- Patient Global Impression of Severity (PGI-S) Scale

\*Where possible, all questionnaires should be completed electronically during the clinic visit; if any technical issues occur, or if the participant requests it, paper copies of the questionnaire can be used. If the participant is unable to complete the questionnaires during their clinic visit there will be an option for them to complete at home.

#### 7.8.4. End of study telephone follow up visit

All participants will be contacted via telephone\* at week 35 post-randomisation. During this call, a delegated research team member should ask the participant if they have experienced any adverse events, if there have been any changes to the concomitant medications or if they have been prescribed any additional immunosuppressant or antifibrotic medication. The participant will be asked to self-reported IMP compliance during the weaning phase (see section 8.6.2) The participant can return any unused medication to pharmacy at their next standard of care clinic visit for the purpose of safe destruction as per the hospitals local policy.

#### 7.9. Withdrawal and change in participation status

Participants are free to discontinue from some or all aspects of the trial at any time if they wish to do so, without having to give a reason and without detriment to their ongoing care. In addition, a participant may be withdrawn from any aspect of the trial at the request of a healthcare professional if they feel it is within the best interest of the participant. In accordance with regulatory guidance, trial data that have already been collected will continue to be retained and used in the analysis.

Participants will be able to flexibly change their participation in the trial by selectively withdrawing from one, some or all of the following aspects:

- Discontinuation of allocated trial treatment but continue to attend trial follow up visits
- Discontinue allocated trial treatment and withdrawal from trial follow up visits but allow for passive data collection from medical records

- Withdrawal from the trial completely and explicitly request no further data is collected from their medical records (except where required for reporting of serious adverse events)
- Optional collection of CT scan performed as standard of care and stored with a third party vendor
- Optional collection of a one-off blood samples at baseline and 12 weeks to be shipped and stored to a central laboratory for future genotyping and other mechanistic work
- If they would like to receive trial newsletters
- If they would like to receive the trial results and their allocation at the end of the trial

Participants who withdraw consent for trial participation prior to randomisation will be withdrawn from the trial completely and no further data will be collected. These participants will not count towards the recruitment target.

PeRSEVERE principles will be followed for participants who cease to engage with the trial (see: https://persevereprinciples.org/). If a participant becomes uncontactable and stops engaging with the trial, passive data collection will continue where available from the medical notes unless the participant expressly indicates they wish to fully withdraw from this.

If a participant is not engaging with the trial at a particular follow-up visit, reasonable attempts will still be made to contact them at the next timepoint unless they expressly indicate they wish to withdraw (e.g. if they don't answer their phone at the week 4 timepoint, attempts should still be made to complete the week 8 follow-up call).

If it becomes apparent that a participant has lost mental capacity and is unable to complete a follow-up timepoint, this will be recorded in the eCRF. Participants who lose mental capacity during the trial will be withdrawn in full and their original consent will no longer apply. Data and samples collected up to the point of withdrawal will be retained but no further data or samples will be collected.

All participants who change their participation status, or cease engaging with the trial, will still have the option to receive information about the trial, including newsletters and end of trial results unless they opt not to receive them.

The details and reason for change in participation status will be recorded in the participant's 'Change in Participation' eCRF and medical notes.

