#### 7.9.1. Discontinuation of trial treatment

If a randomised participant decides that they no longer wish to continue receiving trial treatment they should continue their trial follow up visits in accordance with the protocol unless they also request to be withdrawn from this aspect of the trial.

If the participant commenced their allocated trial drug and subsequently chooses to withdraw from trial treatment (or is withdrawn due to loss of mental capacity), it is recommended that the participant completes the weaning period off their medication (see dose schedules in section 8.6). Depending on the dose the participant is receiving at the time of the discontinuation, they may require a slower weaning period; this is at the discretion of the PI or delegated medically trained doctor.

If a participant chooses to withdraw from both trial treatment and follow up visits, passive data collection of safety data and additional therapies for FHP from medical records will be collected where possible unless the participant explicitly requests their medical records are not accessed.

The participant should not be unblinded unless it is considered medically necessary for the participant's safety by a medically qualified doctor.

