#### 9.3. Recording and reporting of Adverse events (AEs)

The safety reporting period will begin from the time of randomisation up to the week 35, End of Study telephone follow-up. The recording and reporting requirements are summarised in the safety reporting flowchart in Figure 5. Adverse events should be reviewed at every follow up visit.

Figure 5: Safety reporting flow chart

All adverse events will be assessed for seriousness and causality as per the definitions in section 9.1 above. These assessments should be carried out by the site PI, or delegated medically qualified doctor, and recorded in the medical notes. If the adverse event is possibly, probably or definitely related to prednisolone it is considered an adverse reaction (AR) and must be reported in the adverse event eCRF in REDCap. In addition to this any viral, fungal or bacterial infections of any kind are considered Adverse Events of Special Interest (AESI) for this trial and must be reported on the adverse event eCRF. If the adverse event doesn't meet the definition of serious and is not considered to be an AESI or AR it should only be documented in the participants medical notes but not be reported on the adverse event eCRF.

All related and unrelated adverse events that are considered serious, as defined in section 9.1, must be reported as an SAE. Additional guidance for reporting serious adverse events can be found in section 9.4 below.

As this is a blinded trial, adverse events should be evaluated on the assumption that the participant was allocated the active drug i.e. prednisolone. The blind should only be broken where knowing the allocation is clearly necessary and will alter the appropriate medical management of the participant. If unblinding is necessary, please refer to the Emergency Unblinding section of the protocol (7.7.1) and the CHORUS 'Unblinding' working instruction.

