### 9.4. Recording and reporting Serious adverse events (SAEs, SARs, SUSARs)

All related and unrelated adverse events that meet the protocol definition

of serious must be reported to ExeCTU

within 24 hours of the PI, delegate or research team becoming aware

by completing the 'SAE' eCRF in REDCap.

All SAE eCRFs must be reviewed and signed off by a PI or delegated medically qualified doctor, within REDCap. In the event of a death, the Death eCRF should be completed *in addition* to the SAE eCRF in REDCap. Any information not available at the time of the initial report (e.g. test results) must be added to the SAE eCRF by the site team as soon as it becomes available.

For each SAE the following information will be collected:

- Full details in medical terms with a diagnosis (if available)
- Event duration (date of onset and date of resolution)
- Reason for seriousness
- Trial drug details
- Action taken
- SAE outcome
- Causality and severity, in the opinion of PI (or medical delegate)

ExeCTU will receive an automated email notification to alert them to a new SAE eCRF or when a change is made to an existing SAE eCRF. In the event of a SUSAR the site will be contacted by the CHORUS trial manager and it may be requested that further details are added SAE eCRF please refer to safety work instruction.

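### After loss of capacity, section 7.9 stops all data collection with no exception for serious adverse events, while section 9 requires SAEs and deaths to week 35; section 7.4 also asks for a preference that 7.9 overrides

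*Protocol*

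**What the plan says.** Section 7.9 sets the rule for loss of capacity in two sentences. The first fixes status: "Participants who lose mental capacity during the trial will be withdrawn in full and their original consent will no longer apply". The second fixes data: "Data and samples collected up to the point of withdrawal will be retained but no further data or samples will be collected". Neither carries a qualification.

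Section 7.9.1 deals with trial drug. It covers a participant who has started treatment and then chooses to stop "or is withdrawn due to loss of mental capacity), it is recommended that the participant completes the weaning period off their medication".

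Section 9.3 sets the safety window: "The safety reporting period will begin from the time of randomisation up to the week 35, End of Study telephone follow-up". Within it, "All related and unrelated adverse events that are considered serious, as defined in section 9.1, must be reported as an SAE". Section 9.4 gives sites 24 hours to report an SAE, sections 9.4.2 and 9.9 require follow-up to resolution or week 35, and section 9.4.3 requires every death in the window to be reported, related or not.

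Section 7.4 says that participants will be asked at consent whether they would prefer to remain or withdraw should they lose capacity, and refers the reader to section 7.9 for the details.

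**The concern.** Taken literally, section 7.9 tells a site to stop recording at the moment of capacity loss, and section 9 tells the same site to go on reporting SAEs and deaths. One site could report a later death under section 9 while another omits it under 7.9. Follow-up of the event that caused the loss of capacity is just as unclear.

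The people concerned may still be exposed to the drug, because the wean is recommended for them. Section 8.7 itself foresees significant psychiatric events attributed to higher prednisolone doses, so the event behind a loss of capacity could be drug-related.

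These reports feed the unblinded DMC safety review (section 9.4.1) and the safety outcome (section 3.3.2, item 10). Section 10.10 also analyses death and hospitalisation by logistic regression and time-to-event methods, and both are SAEs by the definition in section 9.1.

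The second stake is consent: participants are asked to state a choice that the protocol will not act on.

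**Working it through.** The protocol gives no figure on this point, so the check compares the text and then measures the window.

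**1. Does another sentence supply the missing exception?** Two candidates exist.

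- The list of withdrawal options in section 7.9 has an SAE exception. It is worded for participants who withdraw "completely and explicitly request no further data is collected from their medical records (except where required for reporting of serious adverse events"). That describes an explicit request, which a person without capacity does not make.
- Section 7.9.1 provides for passive safety collection: "If a participant chooses to withdraw from both trial treatment and follow up visits, passive data collection of safety data" continues from medical records where possible. This is worded for a participant who chooses to leave. The same section names loss of capacity when it recommends the wean, but not here.

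Neither sentence states that it covers loss of capacity.

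**2. Does section 9 exempt these participants?** Sections 9.3, 9.4, 9.4.2, 9.4.3 and 9.9 were read for a carve-out. None has one. Section 9.4 opens its duty with "All related and unrelated adverse events that meet the protocol definition" of serious, without regard to participation status.

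**3. Result of the comparison**

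| Situation | SAE reporting after withdrawal |
|---|---|
| Participant withdraws completely and asks for no more collection (7.9) | Continues where required |
| Participant chooses to stop treatment and visits (7.9.1) | Continues passively from records, unless access is refused |
| Participant loses capacity (7.9) | None, as worded |
| Any participant (section 9) | Required to week 35 |

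So the participant who expressly refuses further collection keeps SAE reporting, and the one who made no refusal loses it.

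**4. Length of the disputed window.** The reporting period ends at 35 × 7 = day 245. For capacity loss on day d, the rules differ for 245 − d days:

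- d = 0 (randomisation): 245 days = 35 weeks
- d = 84 (week 12): 245 − 84 = 161 days = 23 weeks
- d = 182 (week 26): 245 − 182 = 63 days = 9 weeks
- d = 245 (week 35): 0

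**5. Overlap with drug exposure.** The weeks column of the dose table in section 8.6.1 gives a wean of 1 + 2 + 2 + 2 + 2 = 9 weeks = 63 days. For d ≤ 182, 245 − d ≥ 63, so a wean started at capacity loss and run at the tabulated rate lies wholly inside the disputed window.

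**6. Section 7.4 against 7.9.** Section 7.4 collects a remain-or-withdraw preference and cross-refers to 7.9. Section 7.9 gives that preference no role and withdraws all. The amendment history lists the 7.9 rule as a response to ethics committee feedback and lists no change to 7.4, which suggests that the 7.4 sentence was left behind. The mismatch itself is between the two current sections.

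**The case against.** The strongest reply is that full withdrawal in the capacity rule naturally means the complete-withdrawal option listed earlier in the same section, so its SAE exception carries over. Sites would also tend to follow the specific 24-hour duty in section 9.4 over a general sentence. That may well be the intent. The text does not say it, however: the exception is tied to an explicit request, and the capacity rule adds that consent no longer applies, which gives a cautious site a reason to stop.

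Other points have some force:

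- **Material not seen.** The safety flow chart and weaning algorithm figures are not shown in the text available, and the safety work instruction is a separate document. Any of them might settle practice. They would not remove the conflict in the protocol's wording.
- **The 9-week wean.** It starts from the 10 mg maintenance dose. Someone on 20 to 40 mg may need a slower wean at the investigator's discretion, so the overlap in step 5 holds only at the tabulated rate.
- **The causal event.** If serious, it precedes withdrawal, so it is reportable and its data are kept. Only its later follow-up is open.
- **Size.** The window is calendar time, not a count of lost events. Few participants are likely to be affected, and SAEs as such are only summarised descriptively.

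These limit the size of the problem. None of them answers the 7.4 mismatch.

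**Conclusion.** The concern holds. Sections 7.9 and 9 give opposite instructions on SAEs and deaths after loss of capacity, for between 0 and 245 days depending on when it occurs, and no sentence says which prevails. Section 7.4 asks for a preference that section 7.9 then ignores.

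This rests on reading the current sections as worded, and on the assumption that the number affected is small, since the protocol gives none. No bias in the primary FVC comparison and no difference between arms is claimed. Nor is the withdrawal rule, the wean recommendation, or the end of scheduled visits and non-serious event collection disputed. It should be fixed because the reports at stake are mandatory safety reports, where a single omitted death or SAE matters.

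**What to change.** Keep the withdrawal rule and make three text changes:

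1. **Section 7.9:** after the capacity rule, state that nothing further is collected except SAEs (including follow-up of the event behind the loss of capacity) and deaths, which continue to be reported to week 35. This extends the exception already given for complete withdrawal.
2. **Section 7.9.1:** cross-refer to that exception where the wean is recommended for these participants.
3. **Section 7.4:** delete or correct the sentence on the remain-or-withdraw preference, and align the information sheet and consent form if they carry it.

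No new visits, forms or staff are needed; the SAE and Death eCRFs exist. The cost is one amendment. Because the 7.9 rule answered ethics committee feedback, the committee should see the change. If the sponsor classes it as substantial, sections 15.1 and 15.8 also call for HRA and MHRA approval and the TSC chair's agreement, and sites must be told.
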